$$MAP = \frac{(\text{Diastolic arterial pressure} \times 2) + \text{systolic arterial pressure}}{3}$$

Weight, height and Maternal Body Mass Index (BMI)

Ultrasound examination

- Crown-Rump Length (CRL) (27)
- Mean Uterine arteries Pulsatility Index (UtAPI).
- Umbilical artery pulsatility index (UA-PI), Middle Cerebral Artery Pulsatility Index (MCA-PI) and Cerebro-Placental ratio (CPR).
- Estimated fetal weight centile in 2nd and 3rd trimester, (28)

Blood test samples

PAPP-A will be determine using fluoroinmunoessay in the autoanalyzer DELFIA_Xpress, expressed in multiples of median (MoMs). PIGF will be determine using immunoanalysis electroquimioluminscent automatized in the analyzer Cobas e601 (Roche Diagnostics). sFlt-1 will be determine using immunoanalysis electroquimioluminscent automatized in the analyzer Cobas e601 (Roche Diagnostics).

OUTCOMES

Primary outcomes

Diagnosis of preeclampsia during pregnancy following the definition of the *International Society for the Study of Hypertension in Pregnancy*, (ISSHP)

Secondary outcomes

- Early-onset Preeclampsia: diagnosos before 34 weeks of pregnancy
- Severe preeclampsia (ISSHP)
- Pregnancy-induced hypertension
- Small for gestational age: birth weight below the 10th percentile (29)

- Intrauterine Growth Restriction (IUGR, Delphi procedure Consensus. Gordijn SJ, 2016)
- Perinatal mortality (>22 weeks of pregnancy - < 28 days postpartum).
- Neonatal acidosis (arterial pH <7.10 + base excess >12mEq/L)
- Days of admission in neonatal Intensive Care Unit
- Significant neonatal morbidity: convulsions, intraventricular haemorrhage > III grade, periventricular leukomalacia, hypoxic-ischemic encephalopathy, abnormal electroencephalogram, necrotizing enterocolitis, acute renal failure (serum creatinine >1.5mg/dL) or heart failure (requiring inotropic agents).
- Gestational age at birth
- Type of delivery (vaginal, spontaneous or instrumental, cesarean section)
- The economic cost of the analysis of angiogenic and antiangiogenic factors in euros (PIGF and sFlt-1).

SAMPLE SIZE

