Considering the number of first-trimester ultrasounds that are conducted in the participant hospitals, we estimate that 8200 patients will be potential candidates to participate in the study. Due to PE prevalence in our environment is around 3% of the total population, which means that approximately 246 patients of our sample will develop PE and based on similar previous experiences we could assume that around 80% of the patients will consent to participate in the study, meaning a total sample of 6560 pregnant women.

Based on a pilot study previously performed, we estimate that a 30% of the patients (which means approximately 1968 pregnancies) will be classified as intermediate or high risk after the PE universal screening. This sample size assures enough statistic power and the possibility of extrapolating the results to the clinical practice.

DATA COLLECTION

All the data required to carry out this study, including those derived from sonographies and blood tests, will be collected during the normal pregnancy control, without further appointments. This is one of the most important aspects of this project: developing an efficient

screening of preeclampsia during the first trimester using the explorations and visits that are already included in the pregnancy control.

The data will be collected during normal pregnancy control as follows:

A blood test will be requested in all pregnant women in the first appointment of pregnancy control between 9 and 13 weeks, to determine risk of chromosomal disorders according to the national protocol (*Sociedad Española de Ginecología y Obstetricia, SEGO*). This blood sample will be collected preferentially between 11 and 13 weeks, and it will be used this same sample to analyze angiogenic factors without requiring new blood extractions.

In the first-trimester scan, the mean uterine arteries pulsatility index will be determined, as well as mean arterial pressure. In this visit, the patient will be asked about her medical history. We will offer the patients the inclusion to our study in that moment; those who agree to participate in the study will sign the informed consent.

In patients who do not agree to participate in the sequential screening study, will be classified according to the algorithm without angiogenic factors, in:

Low Risk: (Preeclampsia Risk $<1/250$)

High Risk: (Preeclampsia risk $> 1/250$)

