A bivariate statistical analysis will be performed in order to assess the relationship between dependent variables (diagnose of PE and/or IUGR) and the other variables included in this study. This association will be analyzed using: Continuous variables: Student's t-test; Categorical variables: Contingence tables. The inference will be estimated by means of X² of Exact Fisher's test; Ordinal variables: Mann-Whitney U. Finally, a multivariate analysis will be performed using binomial logistic regression.

Different models will be tested, and two validity indices will be calculated on the final model: goodness of fit (Howmer-Lemeshow test) and discrimination (the area under the ROC curve).

All statistical analyzes will be performed with the IBM SPSS version 20.0 program, and the usual statistical significance level of 0.05 will be established.

ETHICS AND DISSEMINATION

The study will be conducted in accordance with the principles of Good Clinical Practice. The research team will guarantee the accuracy and trustworthiness of the data and reports that could be required, as well as its confidentiality. The investigator will keep all the documents of the study for, at least, 5 years after its conclusion, being available if they were requested by the monitor, auditor, ethics committee or Health Authority.

DISCUSSION

The main limitation of this study is that the data referring to the progress of the pregnancy and the delivery will be collected from the medical history of the patients; there could be errors on its transcription or interpretation and it is possible that some patients may decide to deliver in an another medical center. Contrary, prospective design in a clinical scenario with the participation of different Hospitals provides great extern validity.

FUNDING: This work was supported by Health Institute Carlos III grant number PI19/00692

COMPETING INTERESTS: None declared

ETHICS APPROVAL: This study was approved by the Clinical Research Ethics Committee (CEIC) of Health Research Institute of Aragon (IIS Aragon), on 8th July 2020.

REFERENCES

1. Duley L. The global impact of pre-eclampsia and eclampsia. *Semin Perinatol* 2009;33(3):130-7.
2. Melchiorre K, et al. First-trimester uterine artery Doppler indices in term and preterm pre-eclampsia. *Ultrasound Obstet Gynecol* 2008;32(2):133-7
3. Lisonkova S, et al. Maternal morbidity associated with early-onset and late-onset preeclampsia. *Obstet Gynecol* 2014;124 (4):771-81.

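### Student's t-test is named for every continuous variable without addressing unequal variances; with a PE split of about 3:97 its error rate depends on the SD ratio, whatever the sample size

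*Combined protocol and SAP*

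**What the plan says.** The Statistical Analysis section plans a bivariate analysis relating "dependent variables (diagnose of PE and/or IUGR) and the other variables included in this study". For measured quantities the method is "Continuous variables: Student's t-test". Chi-squared or Fisher's exact test is used for categorical variables, and Mann-Whitney U for ordinal ones. The section mentions no variance check, no unequal-variance version and no alternative for continuous variables. It adds that "the usual statistical significance level of 0.05 will be established". Logistic regression follows, and the final model is judged by the Hosmer-Lemeshow test and the area under the ROC curve.

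The size of the PE group follows from the Sample Size section: "PE prevalence in our environment is around 3% of the total population". The same section counts 8,200 candidates, 6,560 participants and 246 PE cases. The continuous variables include baseline measures such as mean arterial pressure, uterine artery pulsatility index and PAPP-A, and outcomes such as gestational age at birth and "Days of admission in neonatal Intensive Care Unit".

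**The concern.** In its usual meaning, Student's t-test pools the two groups' variances. When one group holds 97% of the women, the pooled variance is essentially that group's variance. The true standard error of the difference, however, is driven by the small group. If the two spreads differ, the standard error used is wrong by nearly the SD ratio.

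A large sample is often taken as reassurance for the t-test. It helps against skewness, but not here: the error depends on the SD ratio and the group split, and neither changes as recruitment grows.

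Unequal spread is plausible for some outcomes. The Introduction describes PE as a mixture of uncommon, severe early-onset disease and more frequent, milder late-onset disease. At stake are the p-values, and any confidence intervals, of the bivariate comparisons.

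**Working it through.** **Inputs from the documents.** Candidates 8,200; consent 80%; PE prevalence 3%; intermediate or high risk 30% (Sample Size); alpha 0.05 (Statistical Analysis), taken as two-sided because sidedness is not stated.

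**Assumption.** The SD ratio r (PE divided by non-PE) is not in the documents and is varied from 0.5 to 2.

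**The plan's own figures.** 8,200 × 0.03 = 246; 8,200 × 0.80 = 6,560; 6,560 × 0.30 = 1,968. All reproduce. The 246 is 3% of candidates; 3% of the 6,560 participants is 197. Both splits are used below.

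**Formula.** Set the non-PE SD to 1 and the PE SD to r, with n1 PE and n2 non-PE women.

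- Pooled variance: Sp² = [(n1 − 1)r² + (n2 − 1)] / (n1 + n2 − 2)
- Variance the test uses: Vp = Sp²(1/n1 + 1/n2)
- True variance: Vt = r²/n1 + 1/n2
- True type I error = 2[1 − Φ(1.96 √(Vp/Vt))]

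**Worked case, r = 1.5, 197 vs 6,363.**

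- Sp² = (196 × 2.25 + 6,362)/6,558 = 6,803/6,558 = 1.0374
- Vp = 1.0374 × (1/197 + 1/6,363) = 0.005429
- Vt = 2.25/197 + 1/6,363 = 0.011578
- √(Vp/Vt) = √0.4689 = 0.685, so the standard error used is about two thirds of the true one
- Error = 2[1 − Φ(1.342)] = 18.0%; a nominal 95% interval covers 82.0%

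**All ratios, 197 vs 6,363.** The simulation used 10,000 normal data sets per ratio with equal means.

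| r | SE used / true SE | Pooled, formula | Pooled, simulated | Welch, simulated |
|---|---|---|---|---|
| 0.5 | 1.89 | 0.02% | 0.0% | 4.8% |
| 0.8 | 1.23 | 1.6% | 1.6% | 5.1% |
| 1.0 | 1.00 | 5.0% | 5.3% | 5.2% |
| 1.1 | 0.91 | 7.3% | not run | not run |
| 1.25 | 0.81 | 11.2% | 10.9% | 4.6% |
| 1.5 | 0.68 | 18.0% | 18.9% | 4.9% |
| 2.0 | 0.53 | 30.1% | 30.5% | 4.9% |

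**Sample size.** The Statistical Analysis section also includes women who decline, which gives up to 246 vs 7,954. The formula results are the same to four decimals. At r = 1.5 the error is 18.0% for 30 vs 970, 197 vs 6,363 and 1,970 vs 63,630 alike.

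**PlGF and sFlt-1.** Data Collection restricts these to intermediate- and high-risk women, about 1,968, so 3:97 does not apply. If 148 to 197 PE cases fall in that subset (an assumption; 7.5% to 10%), the error is 10.5% to 10.1% at r = 1.25 and 26.4% to 24.6% at r = 2.

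**The case against.** **No SD is documented.** This stands. A reader might infer that the planned comparisons will show false-positive rates of 12% to 30%. The documents do not support that: those rates need ratios of about 1.28 to 2.0, a ratio of 1.1 gives only 7.3%, and a ratio below 1 makes the test conservative.

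**The likeliest examples are weak for type I error.** Gestational age at birth and neonatal intensive care days may well be more variable in PE, but their means probably also differ, so a false positive is hardly possible. At r = 2 and a true difference of 0.5 non-PE SD, z = 0.5/√0.005702 = 6.6 pooled and 0.5/√0.020462 = 3.5 Welch: the same decision. This stands for p-values. It does not rescue intervals, whose coverage is wrong whatever the true difference, although the plan does not specify intervals for these comparisons. For the screening predictors, nothing in the documents indicates which SD is larger.

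**The 3:97 split is not universal.** This stands. PlGF and sFlt-1 are measured in a subset, and no IUGR prevalence is given.

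**The plan may not mean the pooled version, and SPSS prints both.** The plan does not mention variances. But the named test is ordinarily the pooled one, and leaving both rows available without naming one leaves the choice until after the results are seen.

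**The consequence is small.** This stands. A reader might infer that the screening model's performance is compromised. It is not: risk classes come from existing software and cut-offs, logistic regression and ROC area do not use this test, and the plan does not say that bivariate p-values select model variables.

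**Conclusion.** The point holds as a minor, free improvement. The test named for continuous variables does not protect the 5% level when spreads differ, and the PE split of about 3:97 makes it close to maximally sensitive to that. The error can run either way: about 7% to 30% at assumed SD ratios of 1.1 to 2, and about 1.6% at 0.8. The size rests entirely on those assumed ratios, with normal data in the simulation; the direction for any particular variable cannot be settled from the documents. Sample size does not alter it.

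The effect is limited to bivariate p-values and any accompanying intervals. For IUGR the size cannot be calculated.

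A reader might also infer that moving continuous variables to Mann-Whitney U, or log-transforming the markers, would be the remedy. Neither follows. With 197 vs 6,363 and equal means and medians, Mann-Whitney rejected in 8.6%, 10.6% and 14.0% of 2,000 simulated normal data sets at ratios 1.25, 1.5 and 2, and the documents describe no marker distribution.

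**What to change.** In the Statistical Analysis section, replace Student's t-test with Welch's (unequal-variance) t-test for continuous variables, and state that p-values and any confidence intervals are taken from the SPSS row for equal variances not assumed. Apply this to every such comparison, without a preliminary variance test.

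The cost is one line of wording. No additional data, patients or software are needed. When the spreads are equal almost nothing is lost: Welch rejected in 5.2% of simulations at ratio 1.

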The aim of this study is to evaluate prospectively, for the first time and in a clinical scenario, a population sequential screening of preeclampsia, saving the determination of angiogenic factors (PlGF, sFlt-1) to a subgroup of patients with an intermediate risk after the first step of the screening, maintaining a high detection rate but with a lower economic cost.

National and international groups working on preeclampsia

Preeclampsia is one of the most important research topics in maternal-fetal medicine, being the screening of this disease the most important point of interest due to its high clinical impact. [name] (PI of Hospital de la Santa Creu I Sant Pau research group) is an international leader in preeclampsia. All the Hospitals participating in this study have worked, in the last years, on different projects focused on preeclampsia and placental insufficiency, some of them collaborating between them (PI16/00375) (MSC EC10-205). Besides, these investigation groups share research lines with the most important international groups working on PE at this moment: Kings College (London), Oxford University, Johns Hopkins University and Charité University Medicine (Berlin).

HYPOTHESIS

Primary hypothesis

It is possible to perform a sequential population screening of PE, saving the determination of angiogenic markers (PIGF+/- sFlt-1) for the subgroup of patients with an intermediate risk of having PE, maintaining a high rate of detection of PE but with a lower economic cost.

Secondary hypothesis

sFlt-1 measurement increases the PE detection rate during the first trimester of pregnancy if determined at subgroups at risk.

Universal PE screening during the first trimester without angiogenic factors (medical history + MAP + UTPI + PAPP-A) selects effectively those patients with a high or intermediate risk of having PE without increasing the cost of the assistance. Sequential population screening of PE presents a similar detection rate of IUGR but with a lower economic cost.

OBJECTIVES

Primary objectives

To determine prospectively, in a clinical scenario, the predictive and preventive capacity of a sequential screening of PE in the first trimester of pregnancy; determining Placental Growth Factor (PIGF) only in those patients classified as intermediate risk after the universal screening without angiogenic factors: medical history, Mean Arterial Pressure (MAP), Pregnancy-Associated Plasma Protein-A (PAPP-A), Uterine Artery Pulsatility Index (UTPI).

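### The AUC of any refitted logistic model will be optimistic, because models are chosen, fitted and assessed on the same women with no internal validation

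*Combined protocol and SAP*

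**What the plan says.** The Statistical Analysis section starts with bivariate tests of "the relationship between dependent variables (diagnose of PE and/or IUGR) and the other variables included in this study". It then moves to binomial logistic regression and states: "Different models will be tested, and two validity indices will be calculated on the final model". The indices are the Hosmer-Lemeshow test and the area under the ROC curve, in SPSS 20 at a 0.05 level. There is no selection rule, no fixed list or limit of candidate predictors, and no form of internal or external validation here or elsewhere in the document.

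The Control Variables section lists more than 20 items as predictive variables. They include fetal weight centiles from the second and third trimesters, which cannot enter a first-trimester screen.

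The Data Collection section describes something different. Women are classified by existing laboratory-validated software at preset cut-offs: 1/500 and 1/50 at the first step, then 1/160 after PlGF in the intermediate group. PlGF and sFlt-1 are measured only in intermediate- and high-risk women. sFlt-1, and PlGF in high-risk women, are left for analysis at the end of the study.

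The primary objective is the predictive and preventive capacity of the sequential screen. A secondary hypothesis is that "sFlt-1 measurement increases the PE detection rate during the first trimester of pregnancy if determined at subgroups at risk".

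**The concern.** An AUC computed on the women who were used to choose and fit a model measures how well the model describes that sample, not how well it will predict in new women. Trying several models and estimating many coefficients both push it upward on average. A Hosmer-Lemeshow test on the fitting data does not reveal this.

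The AUC of the final model is the only discrimination measure that the Statistical Analysis section names. It mentions neither detection rate nor false-positive rate, and does not say whether the fixed algorithm or a refitted model answers the primary objective. The documents give no fixed algorithm or cut-off for sFlt-1, so the sFlt-1 question falls to the refitted models, in a subset with fewer events. There the optimism could be as large as a real gain from a marker.

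**Working it through.** **The plan's own figures (Sample Size section).** "we estimate that 8200 patients will be potential candidates to participate in the study"; "PE prevalence in our environment is around 3% of the total population"; "around 80% of the patients will consent to participate in the study, meaning a total sample of 6560 pregnant women"; "a 30% of the patients (which means approximately 1968 pregnancies) will be classified as intermediate or high risk".

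- 8200 × 0.03 = 246, the stated number of cases.
- 8200 × 0.80 = 6560, the stated sample.
- 6560 × 0.30 = 1968, the stated intermediate- or high-risk group.
- The 246 cases belong to the 8200 candidates. The 6560 participants give 6560 × 0.03 = 197.
- Data Collection expects 20% at intermediate risk: 6560 × 0.20 = 1312.

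The documents state no AUC, power or validation figure, so there is nothing further to reproduce.

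**Quantity computed.** Optimism = AUC in the fitting data minus AUC of the same fitted model in independent records.

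**Set-up.** 150 simulated cohorts per scenario, with 150,000 independent records for testing. There were 22 first-trimester candidates (24 with PlGF and sFlt-1), counted from Control Variables, of which 6 were truly predictive. Two strategies were run: the full logistic model, and screening by t-test at p<0.05 followed by backward elimination at p<0.05. Assumed, because the documents do not give them: predictor effects, true AUC (0.78 for all PE, 0.70 in the subsets), and the number of cases in the subsets.

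| Population | Women | Events | Optimism, selected model | Optimism, full model |
|---|---|---|---|---|
| All PE, candidates | 8200 | 246 | 0.007 | 0.017 |
| All PE, participants | 6560 | 197 | 0.007 | 0.019 |
| PlGF/sFlt-1 subset | 1968 | 118 (6%) | 0.029 | 0.059 |
| PlGF/sFlt-1 subset | 1968 | 177 (9%) | 0.022 | 0.046 |
| Intermediate risk only | 1312 | 79 (6.0%) | 0.048 | 0.090 |
| Intermediate risk only | 1312 | 100 (7.6%) | 0.037 | 0.074 |

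A separate run of the full 22-predictor model for all PE at about 190 events gave about 0.025, taken here as the upper end. As an example, the full model with 118 events in 1968 women showed an AUC of 0.726 in its own data and 0.667 in new records.

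**A caution on the last two rows.** The assumed 6.0 to 7.6% lies above the group's upper cut-off of 1/50 (2%). The documents do not say whether the software's risk refers to any PE or to a narrower outcome. If it refers to any PE and is well calibrated, there would be at most 1312 × 0.02 = 26 events, and the optimism would be larger than shown.

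**One uninformative marker.** In 200 simulated cohorts of 1968 women at 6% PE, with 22 predictors of which 6 were real, adding one noise marker changed the apparent AUC by 0.001 on average (95th percentile 0.005). The AUC did not rise in 25% of runs, and the marker reached p<0.05 in 4%.

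**The case against.** The strongest reply is that the study evaluates a rule set in advance. Software and cut-offs are fixed before the cohort's outcomes are known, so the prospective cohort is itself new data for that rule. This stands. A reader might infer that the screen's predictive capacity as a whole will be overstated. The documents do not support that: detection and false-positive rates at the preset cut-offs carry no fitting optimism. What remains is that the Statistical Analysis section never says these rates are the primary evaluation.

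A reader might also infer that adding sFlt-1 will look beneficial simply because in-sample AUC rises with any added variable. The noise-marker check does not bear that out: an average change of 0.001 is negligible, and most of the optimism is shared by the models with and without the marker. The sFlt-1 concern is the inflated absolute AUC and the freedom to try several models.

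Inflation would be larger for early-onset PE: 0.019 to 0.120 in 6560 women at an assumed incidence of 0.3 to 1.0%. But the plan names only PE and/or IUGR as dependent variables and gives no early-onset incidence, so no such model can be taken as planned.

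The sample may also be larger. The Abstract gives 8200 scans per year and recruitment covers 20 months: 8200 × 20/12 × 0.80 = 10,933 participants, and 10,933 × 0.30 = 3280 in the subset. At that size, with 6 to 9% PE, the simulated optimism is 0.014 to 0.036. The Sample Size section treats 6560 as the total, so this is uncertain.

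Finally, aspirin offered to screen-positive women may lower the observed AUC, so the net bias against an untreated population need not be upward. That is a separate bias. The gap between apparent and new-sample AUC under the same care remains.

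**Conclusion.** The concern holds for refitted models: as written, the plan will report an apparent AUC with nothing to correct it. The inflation is small for all PE (about 0.01 to 0.025 with 197 to 246 events). It is material in the PlGF/sFlt-1 subset (about 0.02 to 0.06 in 1968 women) and larger if only intermediate-risk women are modelled (about 0.04 to 0.09 in 1312). The direction and the gradient with falling event numbers are firm. The sizes depend on 22 to 24 first-trimester candidates, the assumed effects and true AUC, and 6 to 9% PE in the subsets.

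This should be fixed, and it is a cheap improvement. It does not threaten the evaluation of the fixed algorithm, provided the plan says that this evaluation is the primary one.

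**What to change.** Amend the Statistical Analysis section as follows.

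1. Name the fixed sequential algorithm at its stated cut-offs as the primary evaluation of predictive capacity, reporting detection rate, false-positive rate and the AUC of its risk score.
2. For any refitted model, including those with PlGF or sFlt-1, fix the candidate predictors before outcomes are seen and limit them to first-trimester items. Report bootstrap optimism-corrected AUC and calibration slope (for example 500 resamples), repeating every model-testing and variable-selection step in each resample.
3. Compare models with and without PlGF/sFlt-1 on the corrected values.

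The cost is about a paragraph of text and some computing, possibly in a package other than SPSS 20. The reported AUCs will be slightly lower. No further data or patients are needed.

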Secondary objectives

To analyze the different risk subgroups of PE during the first trimester of pregnancy in which could be efficient the sequential determination of sFlt-1.

To analyze the diagnostic and economic yield of the universal screening in the first trimester without angiogenic factors (maternal medical history + MAP + UTPI + PAPP-A), used as a tool to identify those patients at high and intermediate risk of having PE.

To determine the predictive and preventive capacity of a PE sequential screening model in the first trimester of pregnancy for IUGR.

To assess the impact of a PE sequential screening in the incidence of the pathology associated with placental insufficiency (PE, IUGR) in our population.

METHODS

Study design

A multicentric prospective cohort study will be conducted within four Spanish hospitals: *Hospital de la Santa Creu i Sant Pau* (Barcelona), *Hospital Universitario de Cruces* (Bilbao), *Hospital Son Llàtzer* (Mallorca) and *Hospital Clínico Universitario Lozano Blesa* (Zaragoza).

ELIGIBILITY CRITERIA

All singleton pregnancies that present to the 12-week scan in the Obstetrics Unit of the participant hospitals, between March 1st 2021 and 30th October 2022, will be included

Inclusion criteria: Singleton pregnancies; Gestational age less than 14 weeks, estimated according to Crown-Rump Length (CRL); Blood sample between 8 and 14 weeks of pregnancy; Patients who accept to participate in the study and sign the informed consent.

Exclusion criteria: Fetus with chromosomal disorders, major congenital malformations or congenital infections diagnosed in the first-trimester ultrasound; Multiple pregnancies; Non-acceptance of participation in the study.

CONTROL VARIABLES

An assigned study code and the inclusion date will be collected in all patients.

Predictive variables

Medical history

- Filiation and demographic data: age, race, socioeconomic status
- Personal history: tobacco consumption, personal history of diabetes, arterial hypertension, renal diseases, autoimmune diseases, genetic or acquired thrombophilia, and the mean arterial pressure the day of the 12-week ultrasound scan.
- Obstetric history: last menstrual period, parity, previous history of PE, use of assisted reproduction techniques in the current pregnancy.

- Treatment with aspirin, heparin or antihypertensives during the ongoing pregnancy.

Physical examination

Mean arterial pressure (MAP) using the formula:

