In the participants, the initial risk of PE will be calculated using maternal medical history, MAP, UTPI and PAPP-A (already used in aneuploidies screening), using the software validated to each laboratory. Patients will be classified into 3 groups:

- Low risk of PE ($<1/500$)
- Intermediate risk of PE (between $1/50$ and $1/500$)
- High risk of PE ($>1/50$)

In those patients classified as intermediate and high-risk, PIGF and s-Flt-1 will be determined from the blood samples kept in biobanks of each hospital according to the current legislation. sFlt-1 results will be analyzed at the end of the study in order to decrease the cost because there will not be used to make clinical decisions. PIGF in high-risk patients will not be considered either to reclassify those patients. In both cases, the diagnostic efficiency will be analyzed at the end of the study.

Patients in the intermediate-risk group (1/50-1/500) will be reclassified after adding PIGF levels in the predictive algorithm in 2 groups: Low risk of PE (<1/160) and High risk of PE (>1/160).

To the patients classified as high risk at any of the steps, will be offered prophylactic treatment with Acetylsalicylic acid (ASA) (150mg/24h) until 36 weeks of pregnancy, if there is not a contraindication.

The cut-off point of high risk after combined PE screening without using angiogenic factors had been obtained from a pilot study performed in *Hospital de la Santa Creu i Sant Pau* and *Hospital Universitario de Cruces*. According to this initial estimate with the selected cut-off point we expect to find 10% of high-risk patients and 20% of intermediate-risk after the first step of the screening. These results are in agreement with those published by other authors (25).

STATISTICAL ANALYSIS

All data from eligible patients, both those who participate in the study and those who reject it and therefore a one-step screening will be performed, will be analyzed.

The entire research team will participate in the recruitment and every team member will be responsible for the data that will be included in the electronic database, predictive variable and outcomes. This database will be anonymous and codified.

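### The plan does not estimate the detection or false-positive rate of its own two-step rule, or account for aspirin offered to women who screen positive

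*Combined protocol and SAP*

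**What the plan says.** The primary hypothesis is that sequential screening is feasible while "maintaining a high rate of detection of PE but with a lower economic cost". The primary objective is to determine "the predictive and preventive capacity of a sequential screening of PE in the first trimester of pregnancy". The primary outcome is preeclampsia (PE) at any gestation: "Diagnosis of preeclampsia during pregnancy following the definition of the" international hypertension-in-pregnancy society.

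The rule is in Data Collection. A first risk, computed without angiogenic factors, is cut at 1/50 and 1/500. The intermediate group is then split again after PlGF is added: "Low risk of PE (<1/160) and High risk of PE (>1/160". Women who are high risk at either step "will be offered prophylactic treatment with Acetylsalicylic acid" unless it is contraindicated.

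Statistical Analysis plans association tests (t-test, chi-square or Fisher, Mann-Whitney) of PE and growth restriction against the other study variables. It then plans a logistic regression, with several models tried, and states that "two validity indices will be calculated on the final model: goodness of fit (Howmer-Lemeshow test) and discrimination (the area under the ROC curve".

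Two other places touch on accuracy. A secondary objective covers the diagnostic and cost yield of the first step alone. Data Collection adds: "In both cases, the diagnostic efficiency will be analyzed at the end of the study". The two cases meant there are sFlt-1, and PlGF in women already at high risk after step one. Neither place names a metric, and neither covers the two-step rule.

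Aspirin appears among the predictive variables, under medical history: "Treatment with aspirin, heparin or antihypertensives during the ongoing pregnancy". It is given no role in the analysis.

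**The concern.** There are two gaps.

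First, the hypothesis concerns how many PE cases a fixed rule finds at fixed cut-offs. The area under the ROC curve (AUC) of a refitted logistic model summarises ranking over all thresholds of a different predictor, and Hosmer-Lemeshow measures that model's calibration. Neither says what share of cases the rule flagged, or what share of unaffected women it flagged. The Introduction reports earlier screening systems as detection at a 10% false-positive rate, so without the same measures this study cannot be compared with them.

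Second, a positive screen triggers an offer of preventive treatment. A woman correctly flagged whose PE is prevented is counted as a false positive. The better prevention works, the worse prediction looks. The objective joins predictive and preventive capacity, and no analysis separates them. A plain detection rate reported without that caveat could be read as the rule's true detection rate.

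**Working it through.** **Inputs from the protocol.** 8,200 candidates, 80% participation and 3% PE prevalence (Sample Size); aspirin effect of 62% on PE before 37 weeks and 90% before 32 weeks (Introduction, Prevention); for earlier models, detection of about 75% before 37 weeks and 90% before 32 weeks, at a 10% false-positive rate (Introduction, justification of the project).

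**Inputs assumed.** True detection D, aspirin effect E on the outcome considered, and uptake u among screen-positive women. Further assumptions are that the 3% prevalence is free of aspirin effect, uptake is unrelated to PE risk among screen-positive women, and aspirin has no effect in screen-negative women.

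**Plan's own figures.** 8,200 × 0.80 = 6,560 and 8,200 × 0.03 = 246; both reproduce. The 246 is 3% of candidates. Among participants, 6,560 × 0.03 = 196.8, about 197 cases, leaving 6,363.2 non-cases.

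**Formulas.**
- Observed detection o = D(1 − uE) / [D(1 − uE) + 1 − D]
- Cases left = 196.8 × (1 − D·u·E)
- Observed PPV (positive predictive value) = true PPV × (1 − uE)
- Observed false-positive rate (FPR) = (false positives + prevented cases) / (non-cases + prevented cases)

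**All PE, D = 0.75, u = 1, true FPR assumed 10%.** True positives are 0.75 × 196.8 = 147.6 and false positives are 0.10 × 6,363.2 = 636.3, so the true PPV is 147.6 / 783.9 = 18.8%.

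| E (assumed) | Prevented | Cases left | Observed detection (Wilson 95% CI) | PPV | FPR |
|---|---|---|---|---|---|
| 0 | 0 | 196.8 | 75.0% (68.5–80.5) | 18.8% | 10.0% |
| 0.10 | 14.8 | 182.0 | 73.0% (66.1–78.9) | 16.9% | 10.2% |
| 0.30 | 44.3 | 152.5 | 67.7% (60.0–74.6) | 13.2% | 10.6% |
| 0.62, illustration only | 91.5 | 105.3 | 53.3% (43.8–62.5) | 7.2% | 11.3% |

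For E = 0.30: 0.75 × 0.70 = 0.525, and 0.525 / (0.525 + 0.25) = 67.7%.

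**Other values.** With u = 0.7 and D = 0.75, observed detection is 73.6%, 70.3% and 62.9% for the three effects. With D = 0.60 and u = 1 it is 57.4%, 51.2% and 36.3%; in both sets the last figure, at 62%, is again illustration only.

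**Why E must differ by stratum.** Using the Introduction's own pairs at full uptake, PE before 37 weeks (75%, effect 62%) is observed as 53.3%. PE before 32 weeks (90%, effect 90%) gives 0.09 / (0.09 + 0.10) = 47.4%. At half uptake the figures are 67.4% and 83.2%, so the order of the strata reverses.

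**More recruitment.** The Abstract gives 8,200 as an annual number, and recruitment spans 20 months. Then 8,200 × 20/12 × 0.80 × 0.03 = 328 cases. The interval at 75% narrows to 70.0–79.4%, but the aspirin bias is unchanged.

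**Inverting the bias.** Corrected detection = [o/(1 − uE)] / [o/(1 − uE) + (1 − o)]. With o = 0.5327 and uE = 0.62: 0.5327 / 0.38 = 1.4019, and 1.4019 / (1.4019 + 0.4673) = 0.75. The formula returns D.

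**The case against.** The strongest reply is that the data are there. Contingency tables of PE against the other study variables are planned, and risk group by PE would give the counts. This stands as far as it goes: a reader might infer that the study cannot produce a detection rate, and the documents do not support that. But the tables are planned as tests of association. They come with no rate or confidence interval, and nothing says how the two steps combine into one positive or negative result.

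A second reply is that the aspirin figures are hypothetical. This also stands in part. A reader might infer from the Prevention text that observed detection would drop to 53%. The documents do not support that for the primary outcome: 62% is the figure for preterm PE, the outcome is all PE, and no effect on all PE is given. The 75% also matches an earlier-model figure for PE before 37 weeks, not one for this rule. At an assumed effect of 10% the shift is 2 points, inside the no-effect interval.

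Third, a reader might infer that uptake is already recorded. The aspirin item sits under medical history, which Data Collection says is taken at the first-trimester scan, whereas aspirin is offered after classification. The wording allows either baseline use or later use. No section says that uptake after the offer is collected.

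**Conclusion.** The point holds as an inexpensive improvement. Followed as written, the plan names no estimate of the quantity in its primary hypothesis; that conclusion needs no assumption.

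The direction of the aspirin bias follows from the design if aspirin prevents any PE in screen-positive women: observed detection and PPV fall, and FPR rises slightly. Its size is unknown. For all PE, with D = 75% and full uptake, it is about 2 points at an assumed 10% effect and about 7 points at 30%. The 22-point gap at 62% is an illustration, not an expectation. These sizes rest on the assumed D, E and u, on a 3% prevalence without aspirin, and on no aspirin effect in screen-negative women. A single effect for all gestational ages would conflict with the protocol's own two figures.

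**What to change.** 1. Make the primary analysis the detection rate and FPR, with PPV and NPV (negative predictive value), of the two-step rule as applied, with 95% confidence intervals, in participants with a known PE outcome. Count women at low risk after step one as screen-negative.
2. Report how many participants have an unknown outcome; the Discussion already notes that some may deliver elsewhere. Tabulate women who decline, screened by the one-step 1/250 rule, separately.
3. Report the same measures for PE before 34 weeks (the early-onset definition under Outcomes). Add before 32 and before 37 weeks if gestational age at diagnosis can be taken from the records.
4. State that all rates are observed under aspirin offered to screen-positive women.
5. Add a sensitivity analysis with the correction formula shown in the working. Set E separately for all PE and for each stratum, vary u over a stated range, and list the assumptions. To correct FPR and PPV, move the implied prevented cases, observed true positives × uE/(1 − uE), from false to true positives.
6. Use recorded aspirin use to inform u only if that item captures use after the screening result. Otherwise treat u as assumed.
7. Label the logistic models and their AUC as secondary.

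The cost is SAP wording and a short analysis, plus some data extraction if uptake or gestational age at diagnosis is not already captured. Case numbers in the strata will be small, and corrected rates will depend on the assumed E and u.
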